**Figure 1.2-1 Trial Design Schematic**

### 1.3 Schedule of Assessments

	Screening Period		Treatment Period														Follow-up Period (28 days after the final IMP administration)
	Rollover Subjects	Newly Enrolled Subjects															
Visit (Week)	-4 a	-2	0 b	4	8	12	16	20	24	28	32	36	40	44	48	52/ Discontinuation c	56
Trial Day	-28 ± 3	-14 ± 7	1	29 ± 7	57 ± 7	85 ± 7	113 ± 7	141 ± 7	169 ± 7	197 ± 7	225 ± 7	253 ± 7	281 ± 7	309 ± 7	337 ± 7	365 ± 7	393 ± 7
Informed consent d	●	●															
Eligibility assessment	●	●	●														
Demographics		●															
Physical examination	●	●	●	●	●	●	●	●	●	●	●	●	●	●	●	●	●
Body weight		●	●	●		●		●	●	●		●		●		●	●
Endocrine test (TSH), virus test (HBsAg, HCV antibody)		●															
Vital signs e	●	●	●	●	●	●	●	●	●	●	●	●	●	●	●	●	●
12-Lead ECG f		●	●			●			●			●				●	
Clinical laboratory tests g	●	●	●	●	●	●	●	●	●	●	●	●	●	●	●	●	●
Fasting lipids h, i	●	●	●	●	●	●	●	●	●	●	●	●	●	●	●	●	
HbA1c i		●	●			●			●			●				●	
hsCRP, apo B l			●			●			●			●				●	
Confirmation of use of concomitant medications/therapies	←																→
Adverse events	←																→
Pregnancy test j		●	●			●			●			●				●	
Blood sampling for DNA storage k			○														
Dispensing of IMP			●	●	●	●	●	●	●	●	●	●	●	●	●		
Provision of subject diary			●	●	●	●	●	●	●	●	●	●	●	●	●		
Collection of unused IMP and subject diary				●	●	●	●	●	●	●	●	●	●	●	●	●	

● Mandatory; ○ Optional

- aThe results of the scheduled tests performed at Week 8 in the phase 3 confirmatory trial (Protocol No. 346-102-00002) will be used.
- bBody weight and 12-lead ECG will not be required on Day 1 if they have been performed within 7 days prior to Day 1 in the screening period. The results of the scheduled tests performed at Week 12 in the phase 3 confirmatory trial (Protocol No. 346-102-00002) will be used for rollover subjects.
- cIn cases of early discontinuation during the treatment period, the same assessments as in Week 52 are to be performed at Discontinuation Visit within 2 days after the last dose of the IMP as far as possible.

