3.4 Trial Visit Window

For the efficacy and safety endpoints (except for AEs), acceptable windows of analysis visits will be set, and the analysis will be based on the analysis visits, regardless of the time points recorded in the case report form (CRF). Analysis visits will be specified based solely on fasting data for non-HDL-C, TC, HDL-C, TG, and LDL-C (calculated using the Friedewald formula) among the fasting lipid parameters for the efficacy endpoints. The handling of fasting data is described in [Section 5.3](#).

Acceptable windows of analysis visits are shown in [Table 3.4-1](#). The start day of investigational medicinal product (IMP) administration is defined as Day 1. Baseline is defined as the last data before the start of IMP administration. If multiple data points are available for a certain acceptable window, the last data point will be used for the analysis. Data collected more than 2 days after the last IMP administration will be excluded. The last data obtained between the initial IMP administration and 2 days after the last IMP administration will be defined as the Last Visit.

Table 3.4-1 Acceptable Windows of Analysis Visits	
Week	Trial Day Interval
Baseline	- 1
Week 4	2 - 43
Week 8	44 - 71
Week 12	72 - 99
Week 16	100 - 127
Week 20	128 - 155
Week 24	156 - 183
Week 28	184 - 211
Week 32	212 - 239
Week 36	240 - 267
Week 40	268 - 295
Week 44	296 - 323
Week 48	324 - 351
Week 52	352 - 375
Last Visit	Last data obtained between the initial IMP administration and 2 days after the last IMP administration in the treatment period
Week 56 (FU)	Time point recorded in the CRF

4 Sample Size

Assuming a withdrawal of approximately 20 subjects during the treatment period, the target number of subjects is set at 120 to ensure that 100 subjects will complete the 1-year treatment to assess the safety of ETC-1002 at 180 mg in long-term administration.

5 Statistical Analysis Datasets

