8.3 Subgroup Analyses

Subgroup analyses will be performed by the following items for the percent change in LDL-C (direct method) from baseline at Weeks 24 and 52. Statin intensity categories and types are shown in [Appendix 6](#). In the data for each statin type, subjects who use multiple medications will be excluded from the summarization.

- Statin response (inadequate response to statins/difficulties in treatment with statins)
- Sex (Male, Female)
- Familial hypercholesterolemia (Yes, No)
- Diabetes mellitus (Yes, No)
- Age (<65 years, ≥65 years and <75 years, ≥75 years)
- Statin use (Yes, No)
- BMI (<25 kg/m², ≥25 kg/m² and <30 kg/m², ≥30 kg/m²)
- eGFR (<60 mL/min/1.73 m², ≥60 mL/min/1.73 m² and <90 mL/min/1.73 m², ≥90 mL/min/1.73 m²)
- LDL-C at baseline (<100 mg/dL, ≥100 mg/dL and <120 mg/dL, ≥120 mg/dL and <140 mg/dL, ≥140 mg/dL)
- Statin intensity (Low-intensity statins, High-intensity statins, No statins)
- Statin type (atorvastatin calcium trihydrate, fluvastatin sodium, pitavastatin calcium, pravastatin sodium, rosuvastatin calcium, simvastatin, no statins)

9 Safety Analyses

For the safety analysis set, the summarization will be performed by rollover, newly enrolled, and overall subjects. Baseline is defined as the last data before the start of IMP administration. The analysis visits will be Weeks 4, 8, 12, 16, 20, 24, 28, 32, 36, 40, 44, 48, and 52, unless otherwise specified. The same analysis will be performed for each statin response (inadequate response to statins/difficulties in treatment with statins). Summarization at the Last Visit will also be performed in addition to summarization at each time point.

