9.3 Clinical Laboratory Data

Among the urinalysis parameters in laboratory tests, those other than pH and specific gravity will be included in the qualitative urinalysis.

For parameters other than the qualitative urinalysis, descriptive statistics of the actual value and change from baseline will be calculated at each time point. For qualitative urinalysis parameters, shift tables at each time point from baseline will be prepared. For parameters other than qualitative urinalysis, measured values will be categorized using

the reference range to “below the lower limit of reference range,” “within the reference range,” and “above the upper limit of reference range,” and shift tables at each time point from baseline will be prepared.

The number and percentage of subjects meeting the criteria for identifying laboratory values of potential clinical relevance ([Appendix 2: Criteria for Identifying Laboratory Values of Potential Clinical Relevance](#)) and Hy’s law ([Appendix 7: Criteria for Hy’s Law](#)) after IMP administration will be calculated. All data obtained after IMP administration during the treatment period will be analyzed, including those obtained at unscheduled visits.

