9.6 Electrocardiogram Data

For ECG parameters (heart rate, PR interval, RR interval, QRS interval, QT interval, and QTcF), descriptive statistics of the actual value and change from baseline will be calculated at each visit (Weeks 12, 24, 36, and 52).

The number and percentage of subjects with an actual value of QTcF of >450 ms, >480 ms, or >500 ms at any postdose time point will be calculated. In addition, the number and percentage of subjects with a change from baseline in QTcF of >30 ms or >60 ms at any postdose time point will be calculated. All data obtained after IMP administration will be analyzed, including those obtained at unscheduled visits. Similarly, the number and percentage of subjects meeting these criteria at each postdose time point will also be calculated.

For assessment of normality/abnormality, shift tables at baseline and each time point will be prepared.

The number and percentage of subjects meeting the criteria for identifying ECG measurements of potential clinical relevance ([Appendix 3: Criteria for Identifying ECG Measurements of Potential Clinical Relevance](#)) after IMP administration will be calculated. All data obtained after IMP administration will be analyzed, including those obtained at unscheduled visits.

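### The SAP's 2-day post-dose cutoff contradicts its own Week 56 row and its ECG and weight rules, so follow-up and late discontinuation values are missing from the non-AE safety tables

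*SAP*

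**What the plan says.** SAP 3.4 states its scope: "For the efficacy and safety endpoints (except for AEs), acceptable windows of analysis visits will be set". It then sets the cutoff: "Data collected more than 2 days after the last IMP administration will be excluded". The Last Visit definition uses the same limit. Yet Table 3.4-1 in that section has a row for Week 56 (FU), assigned not by a day interval but by "Time point recorded in the CRF".

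The safety sections define their data in three ways:

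- The opening of SAP 9, for by-visit summaries: "The analysis visits will be Weeks 4, 8, 12, 16, 20, 24, 28, 32, 36, 40, 44, 48, and 52, unless otherwise specified". Last Visit is added; Week 56 is not. SAP 9.7.1 gives body weight its own list, which also ends at Week 52.
- SAP 9.3 (laboratory relevance criteria and Hy's law) and 9.4 (vital-sign criteria): "All data obtained after IMP administration during the treatment period will be analyzed, including those obtained at unscheduled visits".
- SAP 9.6 (QTcF categories and ECG criteria) and 9.7.1 (weight criteria): "All data obtained after IMP administration will be analyzed, including those obtained at unscheduled visits". The footnotes to Appendix 1 (vital signs and weight) and Appendix 3 (ECG) nevertheless require an on-treatment value.

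No table title in Appendix 8 names follow-up or Week 56.

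In the protocol's Schedule of Assessments, Week 56 carries laboratory tests, vital signs and body weight, but no ECG. Subjects who stop early have the Week 52 assessments "at Discontinuation Visit within 2 days after the last dose of the IMP as far as possible". Protocol 9.4.2.2 plans laboratory summaries and relevance counts without any post-dose cutoff, and SAP 14 declares no change to the planned analyses.

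**The concern.** A 2-day limit suits an efficacy analysis, where off-drug lipid values would dilute the effect. For laboratory safety it works against the purpose. A subject who stops because of a rising ALT or CK may reach the highest value, or a bilirubin rise, after the last dose. Those values come disproportionately from subjects who stopped, so leaving them out is not neutral: the incidence tables can only under-count.

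The Week 56 visit is also the only scheduled off-drug measurement. Protocol 2.3 relies on uric acid falling after discontinuation in earlier trials. This trial collects the data to show the same for uric acid, creatinine or hemoglobin, but plans no table for it.

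Finally, because the sections disagree, the set of values behind the Hy's law table depends on how the programmer reads them.

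**Working it through.** **Inputs.** 120 subjects treated, about 20 withdrawals, 100 completers (Protocol 9.1, SAP 4). Follow-up visit 28 ± 7 days after the last dose (Protocol 1.3.3). Visit schedule from Protocol 1.3. Data rules as set out above.

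**Plan's own figure.** 100 + 20 = 120, which reproduces the target. Expected withdrawal is 20/120 = 16.7%. The sample size is not at issue.

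**Week 56 against the cutoff.** 28 − 7 = 21 and 28 + 7 = 35 days after the last dose. Since 21 > 2, no Week 56 value can survive the rule, and the Week 56 (FU) row is empty if the rule is applied literally.

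**How much of a completer's data this is.** Laboratory tests are scheduled at 13 post-baseline visits from Week 4 to Week 52, plus Week 56. The visit without a summary is 1/14 = 7.1% of the scheduled post-baseline laboratory visits. Scheduled post-baseline ECGs are at Weeks 12, 24, 36 and 52, so none is lost at Week 56.

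**Where each kind of value ends up:**

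| Value | By-visit and Last Visit summaries | Criteria counts |
|---|---|---|
| Week 56 laboratory, including Hy's law | Out (3.4; not in the Section 9 list) | Out (9.3: treatment period only) |
| Week 56 vital signs | Out (same reasons) | Out (9.4: treatment period only) |
| Week 56 body weight | Out (9.7.1 list ends at Week 52) | Unclear: 9.7.1 includes it; 3.4 and the Appendix 1 footnote point the other way |
| Late Discontinuation Visit, laboratory and vital signs | Out (3.4) | Depends on the reading (below) |
| Late Discontinuation Visit, ECG and weight | Out (3.4) | Unclear: 9.6 and 9.7.1 include them; 3.4 and, for the relevance criteria, the Appendix 1 and 3 footnotes point the other way |

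**The two readings for a late Discontinuation Visit.** If 3.4 is a general exclusion, a laboratory value from day 3 or later after the last dose is removed before the Hy's law count. If 3.4 only assigns values to analysis visits, 9.3 governs. Protocol 4.5 then describes the treatment period by evaluation rather than by full dosing, so the value can count. On either reading, follow-up laboratory and vital-sign values do not count.

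**Number of subjects with a late Discontinuation Visit.** The documents give no rate. On the planned withdrawals it lies between 0 and about 20 of 120 (0% to 16.7%). Any narrower range would be an assumption without a source.

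**The case against.** The strongest defence is that the events are captured elsewhere. Adverse events are exempt from the cutoff, are collected to the end of follow-up (Protocol 8.8.2), and have an onset category for the time after treatment ends (SAP 9.2). A laboratory value that is clinically significant, leads to discontinuation or is serious is an adverse event (Protocol 8.8.1). AST or ALT at 3 times ULN with bilirubin at 2 times ULN, the thresholds in SAP Appendix 7, must be reported both as an immediately reportable event and as an adverse event (Protocol 8.8.6). Such events are monitored to Week 56. The laboratory and vital-sign listings in Appendix 9 state no 2-day limit. All of this stands.

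It does not fill the gap in the tables. A post-stop value that crosses an Appendix 2 threshold without being judged clinically significant need not become an adverse event. A hepatic adverse event does not thereby enter the Hy's law table. Listings give neither an incidence nor a by-visit summary.

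The cutoff also has a proper use. Without it, a Discontinuation Visit held well after the last dose would fall by trial day into one of the Table 3.4-1 windows and be averaged with on-drug values. That supports keeping it for on-treatment summaries, but not for the counts.

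A reader might go further and infer that "If multiple data points are available for a certain acceptable window, the last data point will be used for the analysis" hides abnormal results behind normal retests. This affects only by-visit means and shift tables. The criteria counts use all values, unscheduled ones included, and a retest can also be worse. It is a matter of preference, not part of this point.

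**Conclusion.** The SAP contradicts itself on which post-dose safety values are analysed, and applying it as written under-counts post-stop abnormalities in the tables that serve the primary objective. Week 56 laboratory, vital-sign and weight values, scheduled for up to 120 subjects, enter no by-visit summary; the laboratory and vital-sign values enter no criteria count either. Late Discontinuation Visits add between 0 and about 20 subjects whose final values leave the by-visit and Last Visit summaries. Whether they also leave the Hy's law and other criteria counts depends on the reading. The range assumes that withdrawals run as planned.

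Three stronger conclusions are tempting but not supported:

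- That all post-dose laboratory, ECG and vital-sign data are discarded: SAP 9.6 and 9.7.1 say the reverse for ECG and weight, and no ECG is scheduled at Week 56.
- That Week 56 data are lost to the trial: they are listed, and Table 3.4-1 keeps a row for them, so the text is contradictory rather than a clear discard.
- That a Hy's law case arising after the last dose would go unseen: it is a mandatory immediate report and an adverse event.

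The loss is from the summary and incidence tables only.

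**What to change.** 1. In SAP 3.4, limit the 2-day exclusion to efficacy endpoints and to on-treatment by-visit and Last Visit safety summaries, and state that the Week 56 (FU) row is exempt.
2. In SAP 9.3, 9.4, 9.6 and 9.7.1, use one rule: count potential-clinical-relevance, QTcF-category and Hy's law events over all values from first dose through follow-up, each flagged on-treatment (up to 2 days after the last dose) or post-treatment. Align the Appendix 1 and 3 footnotes with it.
3. Add Week 56 to the laboratory, vital-sign and body-weight by-visit tables, and reflect this in Appendix 8.
4. Optionally, add a shift table from baseline to worst post-baseline value. The last-in-window rule need not change.

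The cost is SAP wording, one programming flag and some extra table rows; the data are already scheduled for collection. The drawback is that some off-drug values enter the counts. The flag handles this, because the on-treatment count can be shown separately.

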5.1 Efficacy Analysis Set

The efficacy analysis set will include subjects who receive at least one dose of the IMP during the treatment period, and who have LDL-C (direct method) measurements at baseline and at one or more time points after IMP administration during the treatment period.

5.2 Safety Analysis Set

The safety analysis set will include subjects who receive at least one dose of the IMP during the treatment period.

5.3 Handling of Missing Data

Missing data will not be imputed.

Fasting lipid parameters will be handled as shown in the table below with regard to fasting conditions.

Fasting Lipid Parameters	Handling of Data
LDL-C (direct method)	Parameter to be used in the analysis, irrespective of fasting conditions
non-HDL-C, TC, HDL-C, TG, LDL-C (Friedewald formula)	Parameters to be used in the analysis only when obtained under fasting conditions

6 Primary and Secondary Outcome Variables

There are no primary or secondary outcome variables.

7 Disposition and Demographic Analysis

7.1 Subject Disposition

For consenting subjects, the number of subjects who provide informed consent and the number of screening failures will be summarized by rollover, newly enrolled, and overall subjects.

For subjects with IMP administration, the number and percentage (using the number of subjects with IMP administration as the denominator) of those who complete the trial and those who withdraw from the trial, as well as the reasons for withdrawal will be summarized by rollover, newly enrolled, and overall subjects.

For subjects with IMP administration, the number and percentage of subjects included in each analysis set will be summarized by rollover, newly enrolled, and overall subjects.

The same analysis will be performed for each statin response (inadequate response to statins/difficulties in treatment with statins; the same, hereinafter).

7.2 Demographic and Baseline Characteristics

For each analysis set, descriptive statistics (number of subjects, mean, standard deviation, median, minimum, and maximum; the same, hereinafter) of age, height, body weight, body mass index (BMI), and estimated glomerular filtration rate (eGFR), and frequency distributions of age groups (<65 years, ≥65 years and <75 years, ≥75 years), categorized BMI (<25 kg/m², ≥25 kg/m² and <30 kg/m², ≥30 kg/m²), categorized eGFR (<60 mL/min/1.73 m², ≥60 mL/min/1.73 m² and <90 mL/min/1.73 m², ≥90 mL/min/1.73 m²), sex, race, ethnicity, country, presence/absence of past medical history, and presence/absence of complications will be summarized by rollover, newly enrolled, and overall subjects.

The same analysis will be performed for each statin response.

7.3 Baseline Disease Evaluation

For each analysis set, descriptive statistics of baseline LDL-C level and frequency distributions of LDL-C level category at baseline (<100 mg/dL, ≥100 mg/dL and <120 mg/dL, ≥120 mg/dL and <140 mg/dL, ≥140 mg/dL), presence/absence of hypercholesterolemia, presence/absence of familial hypercholesterolemia, risk assessment (history of coronary artery disease or familial hypercholesterolemia, high risk, or intermediate risk), presence/absence of diabetes mellitus, and statin response will be summarized by rollover, newly enrolled, and overall subjects.

The same analysis (excluding statin response) will be performed for each statin response.

For subjects with difficulties in treatment with statins in each analysis set, frequency distributions of the reasons treatment was judged to be difficult (muscle impairment, hepatic impairment, renal impairment, cognitive impairment, or other) and the presence/absence of statins with which treatment is judged to be difficult (atorvastatin calcium trihydrate, fluvastatin sodium, pitavastatin calcium, pravastatin sodium, rosuvastatin calcium, or simvastatin) will be summarized by rollover, newly enrolled, and overall subjects.

7.4 Treatment Compliance

For each analysis set, frequency distributions of the IMP compliance rate (<70%, ≥70% to <80%, ≥80% to <90%, or ≥90%) in the treatment period will be summarized by rollover, newly enrolled, and overall subjects. The IMP compliance rate will be calculated using the following formula.

$$\text{IMP compliance rate (\%)} = \frac{\text{Actual number of days taking the IMP}}{\text{Date of last IMP administration} - \text{Date of initial IMP administration} + 1} \times 100$$

The same analysis will be performed for each statin response.

For each analysis set, the number and percentage of subjects who do not change the type and dosage regimen of lipid-lowering drugs, which are mandatory concomitant medications in this trial, throughout the treatment period will be summarized by rollover, newly enrolled, and overall subjects.

The same analysis will be performed for each statin response.

7.5 Prior and Concomitant Medications

For the safety analysis set, frequency distributions of the medications used prior to or during the treatment period, including lipid-lowering drugs, by drug class and preferred term in the World Health Organization Drug Dictionary (WHODD) version Global B3 September 2022 will be summarized by rollover, newly enrolled, and overall subjects.

For each analysis set, frequency distributions of the presence/absence of statin use or ezetimibe use will be summarized by rollover, newly enrolled, and overall subjects. The preferred terms for statins and ezetimibe are shown in [Appendix 4](#).

The same analysis will be performed for each statin response.

7.6 Protocol Deviations

For subjects with IMP administration, frequency distributions of the presence/absence of the following categorized deviations recorded in the CRF will be summarized by rollover, newly enrolled, and overall subjects.

- Dosing
- Inclusion/exclusion criteria
- Met withdrawal criteria but was not withdrawn
- Procedural deviations (affecting primary outcome variables)
- Prohibited concomitant medications

The same analysis will be performed for each statin response (inadequate response to statins/difficulties in treatment with statins).

8 Efficacy Analysis

Efficacy analyses will be performed using the efficacy analysis set, by rollover subjects, newly enrolled subjects, and overall (rollover and newly enrolled) subjects. The analysis visits will be Weeks 4, 8, 12, 16, 20, 24, 28, 32, 36, 40, 44, 48, and 52, unless otherwise specified.

8.1 Efficacy Endpoints

Descriptive statistics of the actual value, change from baseline, and percent change from baseline will be calculated at each time point for LDL-C (direct method). In addition to the summarization at each time point, summarization at the Last Visit will also be performed.

Descriptive statistics of the actual value, change from baseline, and percent change from baseline will be calculated at each time point for non-HDL-C, TC, apo B, hsCRP, and HbA1c. The analysis visits for apo B, hsCRP, and HbA1c will be Weeks 12, 24, 36, and 52.

The number and percentage of subjects whose LDL-C values achieve the lipid management goal based on the risk assessment (<100 mg/dL [history of coronary artery disease or heterozygous familial hypercholesterolemia], <120 mg/dL [high risk], or <140 mg/dL [intermediate risk]) will be calculated at each time point.

The time course of the mean \pm standard deviation for the percent change from baseline in the efficacy endpoints will be plotted.

The same analysis will be performed for each statin response.

